6.2 IMPORTANT PROTOCOL DEVIATIONS

Data discrepancies and deviations from the CTP will be identified for all patients in the database (i.e., enrolled patients). Consistency check listings (for identification of violations of time windows) and a list of protocol deviations will be provided to be discussed at the RPM/DBLM/MQRM. At meetings, it will be decided whether a discrepant data value can be used in analyses or whether it must be queried in the clinical database. Each protocol deviation must be assessed to determine whether it is an IPD. For definition of IPDs, and for the process of identification of these, refer to the BI reference document "Identify and Manage Important Protocol Deviations (iPD)" (2).

If any IPDs are identified, they are to be summarised into categories and will be captured in the Integrated Quality and Risk Management Plan (IQRMP) (3). The following table contains the categories which are considered to be IPDs in this trial. If the data show other IPDs, this table will be supplemented accordingly by the time of the RPM/DBLM/MQRM. Not all IPDs will lead to exclusion from analysis sets. IPDs are indicated as such in [Table 6.2: 1](#).

IPDs will be summarised and listed.

Table 6.2: 1 Important protocol deviations

Category / Code	Description	Comments*	Excluded from ¹
A	Entrance criteria violated		
A1	Inclusion criteria not met		
A1.01	Age out of range	IN02 Also check versus derived age for patient. LABEL: Age < 18	None
A1.01a	Age out of range	IN02 Also check versus derived age for patient. LABEL: Age > 75	None
A1.02	Moderate to severe atopic dermatitis per CTP not confirmed, ie.: BSA of atopic dermatitis involvement at screening < 10% OR BSA of atopic dermatitis involvement at baseline < 10% OR EASI at screening < 7.1 (12 in the CTP as inclusion criterion) OR EASI at baseline < 16 OR IGA at screening < 3 OR IGA at baseline < 3 LABEL: Disease severity out of range (moderate- severe).	IN04 Also check versus BSA, IGA, and EASI	None

Table 6.2: 1 (cont'd) Important protocol deviations

Category / Code	Description	Comments	Excluded from ¹
A1.03	Diagnosis of AD for less than 1 year. LABEL: Disease duration too short.	IN03 Also check versus derived disease duration	None
A1.04	History of inadequate response to topical corticosteroid as judged by the investigator not documented or documented response to topical corticosteroid. LABEL: Lack of inadequate response to topical corticosteroid	IN05 Also manual review versus listing of concomitant therapies (eCRF page, form: Atopic Dermatitis Therapy History (Topical)) and listing of reasons for discontinuation	None
A1.05	Patient is not willing to use a standard emollient for the duration of the study LABEL: Lack of willingness to use an emollient	IN06	None
A1.06	Women of childbearing potential are not ready or able to use highly effective methods of birth control per ICH M3 (R2) that result in a low failure rate of less than 1% per year when used consistently and correctly. LABEL: Not sufficient or no contraception method used	IN07	None
A2	Exclusion criteria violated General Exclusion Criteria		
A2.03	Use of topical corticosteroids (or agent) for atopic dermatitis within 7 days prior to first dose of trial treatment LABEL: Use of topical corticosteroids – wash-out period too short.	EX01 Also manual review versus listing of concomitant therapy used	None

Table 6.2: 1 (cont'd) Important protocol deviations

Category / Code	Description	Comments	Excluded from ¹
A2.04	Use of systemic corticosteroids (or agent) for atopic dermatitis within 4 weeks prior to first dose of trial treatment.	EX02 Also manual review versus listing of concomitant therapy used	None
	LABEL: Use of systemic corticosteroids – wash-out period too short.		
A2.05	Women who are pregnant or plan to become pregnant while in the trial.	EX03	None
	LABEL: Pregnancy.		
A2.06	Currently enrolled or less than 30 days or 5 half lives since participation in another investigational device or drug trial, or receiving other investigational treatment(s).	EX11	None
	LABEL: Participation in another drug development program.		
A2.07	Patient with a transplanted organ (with exception of a corneal transplant > 12 weeks prior to screening) or who have ever received stem cell therapy.	EX04	None
	LABEL: History of transplantation or stem cell therapy.		
A2.08	Any documented active or suspected malignancy or history of malignancy within 5 years prior to the screening visit, except appropriately treated squamous cell carcinoma of the skin or in situ carcinoma of uterine cervix.	EX05 Also manual review versus listing of AEs and listing of medical history	None
	LABEL: Malignancy.		

Table 6.2: 1 (cont'd) Important protocol deviations

Category / Code	Description	Comments	Excluded from ¹
A2.09	Use of any restricted medication as specified in CTP, Table 4.2.3.1:1 or any drug considered likely to interfere with the safe conduct of the study, as assessed by the investigator. LABEL: Restricted medication use.	EX06 Also manual review versus listing of concomitant therapy	None
A2.10	History of allergy/hypersensitivity to the systematically administered trial medication agent or its excipients. LABEL: History of allergy/hypersensitivity	EX07 Also manual review versus listing of medical history	None
A2.11	Active systemic infections (Fungal and bacterial disease) during the last 2 weeks prior to first drug administration, per investigator assessment. LABEL: Washout after systemic infection too short.	EX08 Also manual review versus listing of AEs and listing of medical history	None
A2.12	Relevant chronic or acute infections (exception: common cold) including HIV or viral hepatitis. A patient can be re-screened if the patient was treated and is cured from the acute infection. LABEL: Chronic or acute infection.	EX09 Also manual review versus listing of medical history	None

Table 6.2: 1 (cont'd) Important protocol deviations

Category / Code	Description	Comments	Excluded from ¹
A2.13	
Patients with active TB.
 
Patients with a positive QuantiFERON TB test during screening, if patient had previous diagnosis of active or latent TB and has not completed appropriate treatment per local practice/guidelines within the last 3 years and at least 6 months before first administration of trial medication under this protocol (patients may be re-screened once to meet this criterion).
 
Patients with suspected false positive or indeterminate QuantiFERON TB result may be retested once.
 
If the QuantiFERON TB test result is not available or provides indeterminate results after repeat testing: A tuberculin skin test reaction $\geq 10\text{mm}$ ($\geq 5\text{mm}$ if receiving $\geq 15\text{mg/d}$ prednisone or its equivalent) is considered positive.
 
LABEL: Tuberculosis.
	
EX10
 
Also manual review versus listing of medical history
	None
A2.14	
Evidence of a current or previous disease, medical condition (including chronic alcohol or drug abuse or any condition) other than AD, surgical procedure, psychiatric or social problems, medical examination finding (including vital signs and ECG), or laboratory value at the screening outside the reference range that in the opinion of the investigator is clinically significant and would make the study participant unreliable to adhere to the protocol, comply with all study visits/procedures or to complete the trial, compromise the safety of the patient or compromise the quality of data.
 
LABEL: General health condition.
	
EX12
 
Also manual review versus listing of medical history, vital signs, laboratory results
	None

Table 6.2: 1 (cont'd) Important protocol deviations

Category / Code	Description	Comments	Excluded from ¹
A2.15	
Major surgery (major according to the investigator) performed within 12 weeks prior to first study drug administration or planned during the study.
 
LABEL: Time since major surgery <12 weeks before start of treatment or planned during the study.
	
EX13 Also manual review versus listing of medical history and AEs
	None
A2.16	
Severe, progressive, or uncontrolled hepatic disease, defined as >3-fold ULN elevation in AST or ALT or alkaline phosphatase, or >2-fold ULN elevation in total bilirubin.
 
LABEL: Hepatic disease.
	
EX14 Also manual review versus listing of AEs and laboratory results
	None
B			
B1	
Date of informed consent missing OR No signature available
 
LABEL: IC not available.
	
IN01 In this case: Patient's data will not be used for the reporting in CTR
	All analyses #
B2	
Informed consent too late.
 
LABEL: IC too late.
	
Informed consent date was after V1
	None

Table 6.2: 1 (cont'd) Important protocol deviations

Category / Code	Description	Comments	Excluded from ¹
C	Trial medication and randomisation		
C1	Incorrect trial medication		
C1.01	
Randomisation order not followed
 
Different medication administered at randomization visit, than the patient was randomised to (i.e. drug kit recorded in eCRF is from a different treatment group than the drug kit assigned by IRT)
 
LABEL: Wrong treatment dispensed at randomisation visit.
	
Usually in this case patient should continue with the first medication administered for the whole trial.
	None
C1.02	
Wrong kit assigned to the patient.
 
LABEL: Wrong medication assigned.
	
After unblinding check the numbers of kits assigned by IRT system versus the randomised treatment.
	None
C1.03	
Patient treated without randomisation.
 
LABEL: Treatment without randomisation.
	
Patient treated according to eCRF, but not randomised according to IRT.
	None
C2	Non-compliance		
C2.01	
Non-compliance with study drug administration - administered dose too high
 
LABEL: Too high dose taken
	
The dose administered above 600 mg
	
None

C2.02	
Non-compliance with study drug administration - administered dose too low
 
LABEL: Too low dose taken
	
The dose administered below 600 mg
 
Check versus total infusion volume reported on the eCRF
	
None

Table 6.2: 1 (cont'd) Important protocol deviations

Category / Code	Description	Comments	Excluded from ¹
C3	Incorrect trial medication dispensed		
C3.01	Incorrect trial medication dispensed	This could be e.g. the case if wrong medication was dispensed by investigator at any visit after randomisation visit. After unblinding it needs to be checked whether this is an iP.D.	None
LABEL: Incorrect trial medication dispensed			
D	Concomitant medication		
D1	Previous medication		
D1.01	Washout of previous medication too short	Check versus concomitant medication end date	None #
LABEL: Washout too short.			
D2	Prohibited medication use		
D2.01a	Use of restricted medication (other than steroid) with potential influence on efficacy data	Manual review versus listing of concomitant medication	None #
LABEL: Restricted medication other than steroid.			
D2.01b	Use of restricted medication (systemic steroid) with potential influence on efficacy data	Manual review versus listing of concomitant medication	None #
LABEL: Restricted medication (systemic steroid).			
D2.01c	Use of restricted medication (skin-related steroid) with potential influence on efficacy data	Manual review versus listing of concomitant medication	None #
LABEL: Restricted medication (skin-related steroid).			

Table 6.2: 1 (cont'd) Important protocol deviations

Category / Code	Description	Comments	Excluded from ¹
F	Study specific analysis		
F1	Other trial specific violation		
F1.01	Study drug intake too early (i.e., <14 days after the previous intake) LABEL: Study drug intake outside time window (<14 days)	Check actual visit dates	None
F1.02	Primary endpoint (PE) assessment more than 1 week before planned day LABEL: PE assessment >1 week before planned.	Check actual visit dates versus the scheduled ones	None
F2	Certain violations of procedures used to measure primary or secondary efficacy data		
F2.01	Missing data entries of EASI for Week 4. LABEL: Missing EASI at Week 4.	Missing data for EASI Score— interim analysis.	None
F2.02	Missing data entries of EASI for Week 16. LABEL: Missing EASI at Week 16.	Missing data for PE.	None
F2.03	Patient incorrectly assigned as responder/non-responder for EASI at V7 (in IRT system)	Manual review vs. data entered into the IRT system	None #

Table 6.2: 1 (cont'd) Important protocol deviations

Category / Code	Description	Comments	Excluded from ¹
G Other safety related violations			
G1.01	Pregnancy test not done for woman of child bearing potential per CTP flowchart LABEL: Pregnancy test not done.	Pregnancy test not done at any visit where such is scheduled and the patient did not yet complete follow-up.	None
G1.02	Pregnancy or nursing LABEL: Pregnancy or nursing.	Medical review: Pregnancy or nursing during the trial up to 16 weeks after the last study drug administration	None #

PD will be detected manually; PE = Primary endpoint; IC = Informed consent; IN = Inclusion criterion; EX = Exclusion criterion

Source: BI reference document: “Identify and Manage Important Protocol Deviations (iPD)” [001-MCS-40-413] (2).

¹ See [Section 6.3](#) for population definitions

* tick box on eCRF page and derived data will be checked.

6.3 SUBJECT SETS ANALYSED

The following analysis sets will be defined for this trial:

- Enrolled set (ES)
This patient set includes all patients who signed informed consent. It will be used for display of patient disposition.
- Randomized set (RS)
This patient set includes all patients who were randomized into the trial. It will be used for display of patient disposition, baseline and demographic characteristics, and patients with IPDs.
- Safety analysis set (SAF)
This patient set includes all randomized patients who received at least one dose of study drug. It will be the main analysis set for presentation of safety. Treatment assignment will be based on the actual treatment administered. Actual treatment refers to the actual treatment administered at the first dosing. This treatment should be followed through the whole trial, regardless of the initially randomised treatment.

- Safety analysis set in the open-label treatment period (SAF-OL)
This patient set includes all randomized patients who received at least one dose of study drug and received study medication after re-allocation visit (i.e., after Week 16 visit). Treatment assignment will be based on the actual treatment administered starting from Week 16 visit. This analysis set will be the main set for presentation of the safety data for the treatment re-allocation period.
- Full analysis set (FAS)
This patient set includes all patients in the SAF who had a baseline measurement for the primary endpoint. It will be the main analysis set for presentation of efficacy results. Treatment assignment will be as randomized.
- Full analysis set including completers (FAS-C)
This analysis set includes all patients in the FAS who completed double-blind treatment, i.e., did not prematurely discontinue treatment up to (and including) Week 12.
- Pharmacokinetic parameter set (PKS)
This patient set includes all patients in the SAF who provide at least one evaluable observation for the BI 655130 concentration, which was not flagged for exclusion. This patient set will be used for the display of concentrations.

The discussion of all exceptional cases and problems and the decisions on the allocation of patients to populations will be made at latest at the DBLM.

Handling of Treatment Misallocations in Analysis Sets

If a patient was administered incorrect treatment during the study, then for safety the following will be used in addition:

- If a patient is planned to receive multiple dose administrations of BI 655130 (i.e. randomized to BI 655130 600 mg IV every 4 weeks), then patients will be reported under their actual treatment from the randomisation visit for safety analyses because the overall safety profile is expected to be driven by the amount of drug received in totality over the entire treatment duration. It is not expected that the safety profile will deviate from the planned treatment regimen if the subject receives only one or two vials of the incorrect medication at only some dosing occasions.
- If a patient is planned to receive multiple dose administrations of placebo, then patients will be reported under their randomized treatment group for safety analysis if the patient was administered no vials of BI 655130 at any visit. If the patient was administered at least one vial of BI 655130 during the treatment period, then the patient will be assigned to BI 655130 600 mg IV treatment group.

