3.1 OVERALL TRIAL DESIGN AND PLAN

This is a double-blind, placebo-controlled study assessing the safety, tolerability and efficacy of 600 mg BI 655130 compared to placebo given intravenously every 4 weeks in patients with moderate to severe atopic dermatitis. Safety and tolerability will be evaluated based on AE data collected and physical examination at every visit. At W16 patients will be evaluated for response to treatment by the change in EASI score compared to baseline. Patients who have responded, defined as having attained at least 75% reduction in EASI score compared to baseline will no longer receive treatment and will be followed at W 20, 24 and 28 to evaluate the sustainability of their response. If this patient reaches a 50% reduction in EASI score compared to baseline prior to the planned EOS at Week 28, they will immediately perform EOS and will be given the opportunity to receive treatment in an open label extension trial.

Patients who have not responded, defined as attained less than 75% reduction in EASI score compared to baseline will receive 600 mg BI 655130 at W16, 20, 24 and 28. Patients re-allocated to treatment, who reach EOS will be offered participation in the extension trial if they meet the eligibility criteria.

After re-allocation at Week 16, a patient will know what treatment they are on but will remain blinded to the treatment received until Week 16.

Figure 3.1.1 Trial design

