4.2.2 Emergency procedures

Infusion reactions including anaphylactic reaction

In case of infusion reactions including anaphylactic reaction emerging during or after infusion of trial medication, the investigator should consider in accordance with severity of the reaction and local standard of care to:

- Immediately interrupt the infusion
- Treat with systemic anti-histamines, i.v. steroids, and in case of a severe allergic reaction (eg, anaphylactic reaction) epinephrine

Also draw a plasma sample for IgE and ADA as detailed in the Lab Manual (Central laboratory). Consider also the evaluation of histamine, serum tryptase, and complement components.

In case of infusion reaction, based on patient's clinical course and medical judgment, the infusion may be re-initiated in case of mild or moderate infusion reactions (according to Rheumatology Common Toxicity Criteria (RCTC) V2) at lower speed with gradual increase to complete the infusion as detailed in the Instructions for Preparation and Handling of BI 655130 in the ISF. In any case, the total duration of infusion should not exceed 180 minutes (3 hours).

In case of potential systemic allergic reaction, blood samples for determination of serum tryptase will be collected 0.5 h, 2 h, 6 h, 24 h after onset of the event.

In case of suspected drug related anaphylactic reaction (Appendix [10.1.1](#)) the investigator should discontinue treatment permanently with BI 655130.

Severe infections (according to RCTC V2), serious infections, opportunistic or mycobacterium tuberculosis infections.

Treatment of the infection should be initiated promptly according to local standard of care. No further trial medication should be administered until the active infection has resolved. Treatment with BI 655130 may be restarted when the patient has recovered according to investigator's assessment.

Overall, the choice of Standard of Care treatment will be left at the discretion of the investigator. The sponsor will not provide/supply SoC treatment (s) to the sites.

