6.2.3 Trial Completion and End of Residual Period

For all randomized patients termination of trial medication and trial completion must be recorded on the corresponding eCRF.

For the comprehensive list of the trial procedures required following the end of treatment, please refer to [Flow Chart](#).

Trial Completion:

Trial completion is defined as a patient having reached the EoS visit within the specified window per protocol.

Treatment Completion:

Treatment completion is defined as a patient receiving four (4) infusions of trial drug (BI 655130 or placebo) at V2, V4, V5 and V6.

Proprietary confidential information © 2020 Boehringer Ingelheim International GmbH or one or more of its affiliated companies

In the re-allocation period (V7 to V11) treatment completion is defined as:

- non-responder patient receiving 4 infusions of BI 655130 at V7, V8, V9, V10 and continuing in the trial until the last visit (V11) – End of Study/FU1 (Week 32 - 44).
- responder continuing in the trial until the last visit (V10) – Week 28 or until they reach a 50% reduction in EASI score compared to baseline

Early Treatment Discontinuation:

In case the infusion of study drug is permanently discontinued before the whole amount of prepared solution has been administered to the patient, every effort should be made to keep the patient in the trial and complete all of the remaining study visits. If this is not possible, assessments of the primary endpoint V7 (Week16), should be completed or at a minimum an early EoS visit. Please refer to the [Flow Chart](#).

Early Trial Discontinuation:

A patient not having reached the EoS visit within the specified window per protocol (e.g. due to withdrawal of consent, lost to follow-up, death etc.).

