For the final analysis of the trial to be performed once all patients have completed through the planned period, results will be summarized including the data from the reallocation period (Open-label Treatment phase). Results will be presented separately and in descriptive manner. The time windows for data presentation in this analysis are described in [Table 6.7: 1](#). In addition, analyses including the data from the double-blind period (initially used for the Primary Analysis) will be re-run after the final database lock.

To distinguish between assignment to trial periods/phases and AE assignments, please, refer to [Table 6.1:2](#).

Table 6.1: 2 AE assignment to analysis treatment groups

Randomised treatment	EASI75 response at Week 16	Open-label period	AE assignment to analysis treatment group
PLACEBO	Responder	No Treatment	AE that occurred between first randomised study drug intake and min[(EoS visit date), (last randomised study drug administration date + 112 days)] will be analysed under PLACEBO. AEs occurring later will be listed only.
PLACEBO	Non-Responder	BI 655130 Treatment	AE that occurred between first randomised study drug intake and Week 16 visit date (excluding) will be analysed under PLACEBO. AEs occurring later will be analysed under Open-label BI Treatment.
BI 655130	Responder	No Treatment	AE that occurred between first randomised study drug intake and min[(EoS visit date), (last randomised study drug administration date + 112 days)] will be analysed under BI 655130. AEs occurring later will be listed only.
BI 655130	Non-Responder	BI 655130 Treatment	AE that occurred between first randomised study drug intake and Week 16 visit date (excluding) will be analysed under BI 655130. AEs occurring later will be analysed under Open-label BI Treatment.

Treatment groups up to Week 16 will be labelled as follows:

- **"Speso 600 mg IV q4w"** (i.e., patients randomised to BI 655130 600 mg)
- **"Placebo"** (i.e., patients randomised to Placebo)
- **"Overall Total"** (across treatments: Placebo and BI 655130 600 mg), where appropriate.

Treatment groups for the efficacy analysis after week 16 will be labelled as follows:

- **"Open-label treatment: No Treatment"**
 - **"Placebo"** (i.e., patients randomised to Placebo in the double-blind treatment period and who did not receive an open-label BI 655130 treatment starting from Week 16 (V7))

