 - **"Speso 600 mg IV q4w"** (i.e., patients randomised to BI 655130 in the double-blind treatment period and who did not receive an open-label BI 655130 treatment starting from Week 16 (V7))
 - **"Total"** (i.e., patients randomised either to Placebo or BI 655130 in the double-blind treatment period and who did not receive an open-label BI 655130 treatment starting from Week 16 (V7))
- **"Open-label treatment: Speso 600 mg IV q4w"**
 - **"Placebo"** (i.e., patients randomised to Placebo in the double-blind treatment period and received an open-label BI 655130 treatment starting from Week 16 (V7))
 - **"Speso 600 mg IV q4w"** (i.e., patients randomised to BI 655130 in the double-blind treatment period and received an open-label BI 655130 treatment starting from Week 16 (V7))
 - **"Total"** (i.e., patients randomised either to Placebo or BI 655130 in the double-blind treatment period and received an open-label BI 655130 treatment starting from Week 16 (V7))

Treatment groups for the safety analysis for the whole trial will be labelled as follows:

- **"Speso 600 mg IV q4w"** (i.e., patients randomised to BI 655130 600 mg)
- **"Placebo"** (i.e., patients randomised to Placebo)
- **"Total Speso 600 mg IV q4w OL"** (i.e., patients randomised either to Placebo or BI 655130 600mg and assigned to BI 655130 600 mg open-label treatment at Week 16)

More details on the technical implementation of these analyses are provided in the ADS Plan of this TSAP.

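### SAF-OL counts only study drug given after the Week 16 visit, so a non-responder whose sole open-label infusion is the one at that visit falls outside the main open-label safety set

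*SAP*

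**What the plan says.** **Dosing.** Protocol 3.1 says that patients without an EASI75 response "will receive 600 mg BI 655130 at W16, 20, 24 and 28". Protocol 6.2.3 defines completion of the re-allocation period, for this group, as a "non-responder patient receiving 4 infusions of BI 655130 at V7, V8, V9, V10". V7 is the Week 16 visit, so the first open-label infusion is given at that visit.

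**Membership of the set.** SAP 6.3 builds SAF-OL from randomised patients with at least one dose who "received study medication after re-allocation visit (i.e., after Week 16 visit". The next sentence uses a different boundary: "Treatment assignment will be based on the actual treatment administered starting from Week 16 visit". The set's role is then stated: "This analysis set will be the main set for presentation of the safety data for the treatment re-allocation period".

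**Adverse event assignment.** For a placebo non-responder, SAP Table 6.1: 2 says "AE that occurred between first randomised study drug intake and Week 16 visit date (excluding) will be analysed under PLACEBO". Later events go to the open-label column. The row for non-responders randomised to BI 655130 has the same cut.

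**Other boundaries in the SAP.** The open-label efficacy groups in SAP 6.1 count drug from V7, for example "patients randomised to Placebo in the double-blind treatment period and received an open-label BI 655130 treatment starting from Week 16 (V7". The whole-trial open-label safety column in the same section is defined by assignment at Week 16. Table 6.1: 1 starts the open-label phase on the day after the Week 16 visit. SAP 7.8 bases all safety analyses on SAF, and then assigns SAF-OL to analyses beyond Week 16, with a parenthesis that limits this to patients who do not get open-label drug.

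**The concern.** The membership rule leaves out the visit at which open-label exposure begins. A non-responder who receives the V7 infusion and nothing afterwards has been treated open label but does not qualify for the set that is meant to describe open-label safety. Table 6.1: 2 has by then closed that patient's randomised-arm count. In any table that uses SAF-OL as its population, the patient's events after V7 therefore have no column.

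Whether a patient enters the set depends on receiving a second open-label dose, and tolerability is one possible reason for not receiving it. For placebo non-responders, V7 is also the first planned exposure to BI 655130. In case of a suspected drug-related anaphylactic reaction, Protocol 4.2.2 says "the investigator should discontinue treatment permanently with BI 655130". A patient with such a reaction at V7 would leave both the numerator and the denominator of a SAF-OL table. Safety and tolerability are part of the primary objective and the groups are small (30 and 15 planned), so one patient can change a reported rate.

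**Working it through.** The plan gives no figure on this point. The check compares the rules, with a count of infusions and days.

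**1. Infusions that qualify.** The Flow Chart puts V7, V8, V9 and V10 on Days 113, 141, 169 and 197, which makes 4 planned open-label infusions. Those strictly after the Week 16 visit are Days 141, 169 and 197, which makes 3. The first one does not count towards membership.

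**2. Who is affected.** By plan, anyone who stops between the V7 and V8 infusions: 141 − 113 = 28 days.

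**3. How much follow-up is involved.** Protocol 7.3.4 sets the residual effect period at 16 weeks after the last dose: 113 + 16 × 7 = Day 225. Flow Chart footnote 18 asks that patients who stop early be kept in the visits, or at least be seen 16 weeks after their last treatment. The gap can therefore cover up to 112 days of data, not only the infusion day.

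**4. Where a V7-only non-responder falls under each rule.**

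| Place | Rule (paraphrased) | V7-only patient |
|---|---|---|
| SAP 6.3, SAF | At least one dose | In |
| SAP 6.3, SAF-OL membership | Drug after the Week 16 visit | Out |
| SAP 6.3, SAF-OL treatment assignment | Drug from the Week 16 visit on | Would count |
| SAP 6.1, open-label efficacy groups | Drug from V7 on | In |
| SAP 6.1, whole-trial open-label safety column | Assigned open-label drug at Week 16 | In |
| SAP Table 6.1: 2 | Randomised-arm events end before the Week 16 visit date | Later events go to open label |
| SAP Table 6.1: 1 | Open-label phase starts the day after the visit | The V7 date lies in the blinded phase |
| SAP 7.8 | SAF throughout; SAF-OL beyond Week 16 for those without open-label drug | Unclear |

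One rule, the membership sentence, shuts the patient out. Four others treat the V7 infusion as open label. Table 6.1: 1 and SAP 7.8 add two further conflicts.

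**5. Size, under stated assumptions.** The documents do not allow the number of V7-only patients to be derived. Assume 30 to 40 patients treated open label, one of them V7-only and with the only event of its kind.
- Counting the V7 infusion: 1/30 = 3.3% to 1/40 = 2.5%.
- SAF-OL as written: 0/29 to 0/39 = 0%.

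For the group first exposed at V7, assume that 12 of the 15 placebo patients are non-responders: 1/12 = 8.3% against 0/11 = 0%. The whole-trial open-label safety column pools both randomised arms, so the pooled figures are closer to what would be tabulated.

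The direction is not fixed. If the V7-only patient had no event, dropping that patient would raise the other rates slightly, for example from 3/30 = 10.0% to 3/29 = 10.3%.

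**The case against.** The strongest reply is that the SAP's intent is plain. The set is named for the open-label treatment period, its next sentence starts at the Week 16 visit, and the efficacy groups name V7. A programmer may well include V7-only patients, and SAP 6.3 allows exceptional cases to be settled at the database lock meeting. All this makes a wording slip likely. It does not remove the defect: two adjacent sentences set different boundaries, and a case-by-case decision at lock is weaker than a prespecified rule.

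Three stronger readings are tempting and are not supported.

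- *The events vanish from the report.* They need not. The patient is in SAF, on which SAP 7.8 bases all safety analyses, and in the whole-trial open-label column. Table 6.1: 2 attaches no SAF-OL condition, and SAP 7 lists the individual values of all patients. Because the parenthesis in 7.8 contradicts 6.3, it is not even certain which tables would use SAF-OL.
- *Any infusion reaction at V7 removes the patient.* Protocol 4.2.2 calls for permanent discontinuation only for a suspected drug-related anaphylactic reaction. For mild or moderate infusion reactions it allows the infusion to be resumed. The link between tolerability and exclusion is possible, but narrower than that.
- *Open-label safety is biased downward.* That requires the literal rule to be programmed and at least one V7-only patient to have an event. Neither can be known from the documents.

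It is also fair that Tables 6.1: 1 and 6.1: 2 differ partly by design: SAP 6.1 says that adverse event assignment is to be distinguished from phase assignment. It does not say which boundary SAF-OL follows.

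**Conclusion.** The point holds in limited form. Read literally, SAF-OL omits non-responders whose only open-label infusion is the one at V7, although SAP 6.3 makes it the main set for safety in that period and Table 6.1: 2 no longer counts their events in the randomised arm from the Week 16 visit date. The consequence is confined to tables built on SAF-OL. It consists of a wrong denominator, possible loss of events related to tolerability, and disagreement with the whole-trial open-label column. The number of patients is unknown and may be zero. Under the assumptions shown, one case moves a pooled rate of 2.5% to 3.3% down to 0%. The safety analysis is descriptive, so no test result depends on this. It should still be corrected before the final database lock, because the rule as written does not describe the exposed population.

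**What to change.** Define SAF-OL as all randomised patients who received any full or partial open-label infusion at or after the Week 16 visit (V7). All 4 planned open-label infusions then qualify a patient, in line with the set's own treatment-assignment sentence and the efficacy groups in SAP 6.1.

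In the same edit:
- Reconcile Table 6.1: 1 with Table 6.1: 2 for data dated on the Week 16 visit. Flow Chart footnote 17 places the V7 assessments before the infusion, so these can stay in the blinded phase while events assigned to open label follow Table 6.1: 2. The SAP should say so.
- Correct the parenthesis in SAP 7.8, so that SAF-OL is tied to patients who receive open-label drug, and state which set covers responders after Week 16.
- Footnote the whole-trial open-label column where assignment at Week 16 and actual infusion differ, so that the two denominators can be reconciled.

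The cost is a short text change in three SAP sections (6.1, 6.3 and 7.8) and one dataset flag. It needs no new data and has no statistical downside.
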